The randomized controlled arm of this study aims to demonstrate non-inferiority of the mymobility smartphone (mobile) application (App) with Apple Watch platform in a TJA episode of care, by comparing subjects who receive standard of care (SOC), formal outpatient PT to a study group of subjects who complete remotely guided education and exercise via a mobile application, along with a wearable device. The correlative signature arm will compile key mymobility data, which includes data collected from an Apple Watch, from across the episode of care in TJA to a larger dataset, which will be analyzed to better understand and predict rare events and complications within this population. The purposes of the study are to evaluate the following measures and, as applicable, compare them to the comparator group results:

1. Determine if physical measurements and PROMs are similar between groups
2. Determine if subject satisfaction is higher in the study group
3. Determine the economic benefits to practices, patients and payers
4. Determine if complication outcomes are similar in the study group
5. Determine if the combination of data collected through an episode of care management application on a mobile platform combined with objective physical measurements can be utilized to predict the probability of post-operative complications, discharge disposition, ROM, and other PROM scores. This data set will also be used for future product feature development such as risk stratification, correlative signature modeling, and algorithm development.

VI. Study Objectives

Primary Objectives: The study objectives are to evaluate clinical outcomes, economics, and satisfaction with mymobility and the Apple Watch while developing a correlative heuristic considering multiple endpoints within the THA, TKA and PKA populations. To accomplish the objectives of this multifaceted protocol, the study has been broken into three cohorts with varying objectives. All mymobility study subjects will ultimately be part of the Correlative Analytics cohort. Additional objectives for each cohort are listed below.

A. Pilot & Time Cohort (Cohort I)

Primary Objectives

1. Determine study and product onboarding requirements (time and staff)
2. Determine time required for instrumentation of mymobility App and Apple Watch
3. Determine study execution requirements (time and staff)
4. Verify enrollment assumptions and customized survey content

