 - Should an update of iOS or Watch OS be required, where possible, the update should be completed while the patient is at the site. In some situations, internet connectivity issues can cause significant delays with updating an OS. Under these circumstances the patient may complete the update at home. Additionally, Zimmer Biomet may approve a remote onboarding and watch pairing process for specific sites.
 - Turn on measurements of correct HealthKit data types.

- Review instructions on pairing of the Apple Watch, daily charging instructions, how to look at activity rings, set alerts, and other functionalities.
- iv. At this time, subjects with a compatible model of iPhone will also download the Apple Health and Fitness Recorder App to their iPhone. Following the download, the coordinator and subject will:
- Validate the correct data is being captured from the Apple Watch to the Apple Health and Fitness Recorder App.
- v. Subjects who do not already own an Apple Watch Series 3 or newer will receive one for use in the study.

2. Preoperative Time period (approximately 30 days before surgery)

- i. Subjects will begin to receive mymobility educational material through the App on their phones.
- ii. Collection of mymobility data will begin. This will include within-App questions that are answered by the subject, care plan adherence data and full time HealthKit data collected by the Apple Watch (steps, flights climbed, HR, stand hours) - transferred to the mymobility platform, except for times when the Apple Watch is being charged. At this time, applicable subjects will also have data collected by the Apple Health and Fitness Recorder App.
- iii. mymobility study subjects will follow the entire prescribed pathway of educational content, PROMs surveys, disposition questionnaires, and exercises until day of surgery in addition to their institution's standard of care preoperative procedures including education, classroom work and medical clearances.
- iv. Research coordinators or clinical staff may call subjects to remind them to complete all tasks as directed by mymobility and to confirm that they are charging and wearing the Apple Watch daily, not having problems using mymobility or the Apple Watch, etc. Study subjects will also be provided a direct phone number to the office research coordinator if they have questions regarding the mymobility App or Apple Watch functions.

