A medical event which is considered to be a normal post-operative symptomology or observation following any joint replacement surgery (e.g. joint pain, swelling, decreased range of motion, incisional pain) should not be classified as an adverse event unless it is considered to be more severe, of longer duration, is otherwise more pronounced than is typical, or is serious. Refer to **Section XIII** for the definition of a Serious Adverse Event. Events occurring after the index joint arthroplasty procedure discharge which are determined by the investigator to not be related to the joint arthroplasty procedure, device, use of the mymobility application or Apple Watch, should not be classified as adverse events, regardless of severity or seriousness.

Medical and adverse event collection will begin only after the patient has study surgery.

Specific instructions regarding Medical Events and Adverse Events:

- Readmission is defined as admittance to a hospital following discharge after the index joint surgery. This includes readmissions for observation as well as same day readmission/discharge. Prolonged hospitalization after the index joint surgery is not considered a readmission.
- If multiple medical events are all associated with the same medical issue, then it may be appropriate that only one adverse event is completed, rather than an adverse event for every medical event.
- Knee codes 30 to 60 are to be used for study joint knee events
- Hip codes 70 to 97 are to be used for study joint hip events
- Codes 01 to 29 are general or non-study joint events

*Normal: anticipated/expected in occurrence, severity, and seriousness. If the event does not meet all three criteria, this should be answered "No."

Reporting and Documentation of Adverse Events and Adverse Device Effects

Adverse Events and Adverse Device Effects will be documented on the Adverse Event Report form over the whole time of the investigation including information on the date of onset, treatment and resolution, as well as assessment of both the seriousness and the relationship to the study device. Further, the outcome of complications will be documented and any changes in outcome are to be updated during the course of the study. In case of early termination of the study, further follow-up of the patient shall proceed according to the hospital's standard procedure.

Reporting and Documentation of Serious Adverse Events, Serious Adverse Device Effects, and Device Deficiencies

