Study subject participation is expected to end upon completion of the subject's last follow-up visit (365 days) unless the subject voluntarily withdraws from the study, is withdrawn from the study by the Investigator, is lost to follow-up, undergoes revision to remove the implanted device, or expires. Reason(s) for study completion must be documented on the **Study Completion Form**.

Some patients might not respond to 1 year surveys and can be considered Lost to Follow-up. Surveys completed beyond 18 months postop should not be collected or entered into the EDC.

If the Sponsor decides to terminate the study early, the Sponsor will inform the Investigators of the reason for early study termination. It is the responsibility of the Investigators to inform their IRB/EC as applicable according to local and national laws/regulations.

9. Modification of the Protocol

All amendments to this protocol shall be agreed to by the Sponsor and the Investigator(s) and be recorded with a justification for the amendment prior to

implementation. Approval of the applicable IRB/EC must be obtained prior to implementation, if required according to the local and/or national laws/regulations.

XIII. Safety Management

Adverse events are required to be reported on the Adverse Event Report case report form. The completed Adverse Event Report case report form must be submitted to the Sponsor in a timely manner. The Investigator or Designee will also promptly provide the Sponsor with any additional requested information required for the Sponsor to comply with regulatory requirements. If applicable per their reporting requirements, the Investigator or Designee will also report applicable adverse event(s) to their IRB or EC.

A. Medical Events/Adverse Events Definitions and Classifications

An adverse event is synonymous with complication or medical event. Adverse events will be classified by type, severity, and outcome and may be collected systematically or non-systematically.

The following definitions are from ISO 14155:2020⁽¹⁾.

Classification of the Event

Adverse Event (AE):

An adverse event is any untoward medical occurrence, unintended disease or injury, or untoward clinical signs (including abnormal laboratory findings) in subjects, users or other persons, whether or not related to the investigational medical device and whether anticipated or unanticipated.

Note 1: This definition includes events related to the investigational medical device or the comparator.

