Note 2: This definition includes events related to the procedures involved.

Note 3: For users or other persons, this definition is restricted to events related to the use of investigational medical devices or comparators.

Serious Adverse Event (SAE):

A Serious Adverse Event is any adverse event that led to any of the following:

- a. death.
- b. serious deterioration in the health of the subject, users, or other persons as defined by one or more of the following:
 1. a life-threatening illness or injury, or
 2. a permanent impairment of a body structure or a body function including chronic diseases, or
 3. in-patient or prolonged hospitalization, or

4. medical or surgical intervention to prevent life-threatening illness or injury or permanent impairment to a body structure or a body function;
5. fetal distress, fetal death, a congenital abnormality, or birth defect including physical or mental impairment.

Note: Planned hospitalization for a pre-existing condition, or a procedure required by the protocol, without serious deterioration in health, is not considered a serious adverse event.

Adverse Device Effect (ADE):

An Adverse Device Effect is an adverse event related to the use of an investigational medical device.

Note 1: This definition includes adverse events resulting from insufficient or inadequate instructions for use, deployment implantation, installation, or operation, or any malfunction of the medical device.

Note 2: This definition includes any event resulting from use error or from intentional misuse of the medical device.

Note 3: This includes ‘comparator’ if the comparator is a medical device.

Serious Adverse Device Effect (SADE):

A Serious Adverse Device Effect is an adverse device effect that has resulted in any of the consequences characteristic of a serious adverse event.

Intensity of Symptoms

Mild:

The subject is aware of the sign or symptom, but finds it easily tolerated. The event is of little concern to the subject and/or little clinical significance. The event is not expected to have any effect on the subject’s overall health or well-being.

Moderate:

The subject has discomfort enough to cause interference with or a change in usual activities. The event is of some concern to the subject’s health or well-being and may require medical intervention and/or close follow-up.

Severe:

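### Section XII.D.2 bars post-discharge events judged unrelated from being adverse events, against the protocol's own AE and SAE definitions, so AE-form counts can be incomplete and a comparison of arms biased

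*Combined protocol and SAP*

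**What the plan says.** Section XII.D.2 (Medical Events / Adverse Events) sets the working rule. It concerns "Events occurring after the index joint arthroplasty procedure discharge which are determined by the investigator to not be related to the joint arthroplasty procedure", and then adds the device and the study technology: events unrelated to any of these, including "use of the mymobility application or Apple Watch, should not be classified as adverse events, regardless of severity or seriousness". The same section sends every new medical issue to the Medical Event Log and requires an Adverse Event Form only for those found reportable. Its list of adverse events has three entries: the common complications of joint replacement, events related to the App, Watch, procedure or implant, and manipulation under anaesthesia of the study joint. Only the second depends on relatedness.

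Section XIII.A takes its definitions from ISO 14155:2020, a standard with which the Synopsis claims compliance. An adverse event there is any untoward medical occurrence, "whether or not related to the investigational medical device and whether anticipated or unanticipated". A serious adverse event is an adverse event with a listed consequence, among them death and "in-patient or prolonged hospitalization". The section also states: "An adverse event is synonymous with complication or medical event".

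On timing, Section XII.D.2 says: "Medical and adverse event collection will begin only after the patient has study surgery". The schedule in Section IV has no pre-operative entry for the Adverse Event Form or the Medical Event Log. Yet Section XI.A.2 has app subjects follow content, "disposition questionnaires, and exercises until day of surgery in addition to their institution's standard of care preoperative procedures", from about 30 days before the operation.

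Section V gives as its fourth purpose: "Determine if complication outcomes are similar in the study group".

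**The concern.** Whether an event counts as adverse should not depend on who is thought to have caused it. When relatedness is the entry condition, the count mixes what happened to patients with what investigators believed about it. In an open comparison of an app with usual care, that belief may differ by arm. Only the study arm has the App and Watch, so an investigator weighing a late event has more possible links to consider there than in the control arm.

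Because a serious adverse event is defined as a type of adverse event, the exclusion also reaches serious events. A post-discharge death or hospitalisation judged unrelated would be neither an AE nor an SAE, and would fall outside the SAE reporting in Section XII.D.2. At stake is the comparison of complications in Section V. So is the first Cohort III objective (Section VI.C), whose seven complications include MI, pneumonia and UTI. An investigator could plausibly call any of these unrelated to an earlier knee replacement.

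**Working it through.** **The plan's own figure.** Inputs from Section XVI.B.1: readmission rate 5.4% in both arms, margin 4.5 points, power 80%, alpha 0.05. With unpooled variance and 1:1 allocation:

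n per arm = 2 × p(1 − p) × (z₁₋α + z₀.₈)² / margin² = 2 × 0.054 × 0.946 × (1.960 + 0.842)² / 0.045² = 396.002, rounded up to 397, so 794 in total.

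This matches with one-sided 0.025. One-sided 0.05 would give 312 per arm, or 624. Allowing for 20% loss, 794 / 0.8 = 992.5, consistent with 1,000. Nothing in this calculation uses AE status: the endpoint is all-cause readmission, defined in Section XII.D.2 as admission to hospital after the index discharge.

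**The rules applied to one event.** Take pneumonia with in-patient admission on day 60, judged unrelated by the investigator.

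| Rule | AE? | SAE? |
|---|---|---|
| XIII.A definition | Yes | Yes, in-patient hospitalisation |
| XII.D.2 list (if pneumonia is taken as a common complication, as in VI.C) | Yes | Yes, by XIII.A |
| XII.D.2 exclusion | No | No, because not an AE |
| Medical Event Log | Recorded | Not applicable |
| Chart review (X.H) | Recorded | Not applicable |

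The same event gets opposite answers from current text, twice within one section.

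**What the exclusion does to a comparison.** Let r be the true rate of serious post-discharge events, equal in both arms, and let f_S and f_C be the shares judged related in the study and control arms. The rates recorded as AEs are r·f_S and r·f_C, so the false difference is r(f_S − f_C). The documents give neither r nor the shares. For scale only, set r = 5.4% with 500 per arm (0.054 × 500 = 27 events). This borrows the readmission rate as an assumption and is not an estimate of SAEs.

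| f_S | f_C | Recorded events, study vs control | False difference |
|---|---|---|---|
| 80% | 80% | 21.6 vs 21.6 | 0 |
| 50% | 50% | 13.5 vs 13.5 | 0 |
| 80% | 60% | 21.6 vs 16.2 | +1.08 points |
| 60% | 80% | 16.2 vs 21.6 | −1.08 points |
| 90% | 30% | 24.3 vs 8.1 | +3.24 points |
| 30% | 90% | 8.1 vs 24.3 | −3.24 points |

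Counts fall whenever any event is judged unrelated. A difference between arms appears only if the judgement differs by arm, and it can go either way.

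**Start of collection.** The rule that collection begins after surgery, and the empty pre-operative cells in Section IV, stand against another sentence in Section XII.D.2 that has adverse events and device effects documented throughout the investigation. Section XV.A.5 names rash and pressure sores from the Watch as risks, and study-arm exposure to the Watch begins before surgery.

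**The case against.** The strongest reply is that little is lost. The Medical Event Log takes all new medical problems and non-routine hospital visits after surgery. Chart review at 90 and 365 days separately collects complications, readmissions and ER visits. A death ends participation and goes on the Study Completion Form. A reader might infer that safety data disappear; the documents do not support that. The gap is in classification and tabulation.

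It can also be said that Section XII.D.2 means to separate a reportable subset from a broader log. That reading is workable, but the exclusion says the events are not adverse events at all, not merely that they need no form, so the conflict stands. The decision flowchart is not visible in the text available, so how the steps treat complications or deaths in practice cannot be confirmed.

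A reader might also infer that the plan specifies flawed by-arm safety tables. It does not: Section XVI.A promises only frequencies and percentages of complication data, with no source form or layout. The risk lies in any comparison that uses the Adverse Event Form as its source.

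Finally, it is tempting to say that harm before surgery is invisible. That goes too far, since deficiencies of the App and Watch that could have led to a medical occurrence are reportable with no stated start date, and another sentence covers the whole investigation. These statements conflict and need reconciling.

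The Sponsor's final say on classification does not cure the exclusion. No masked review is described, and an event judged unrelated need not generate a form.

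**Conclusion.** The contradiction is real and is in current text. If the exclusion is followed, AE and SAE counts from the Adverse Event Form will omit serious post-discharge events judged unrelated, and a comparison of complications resting on them could be biased. That the judgement is made with the arm visible is inferred from the design: no masking is described, and only one arm has the App and Watch.

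The size is unknown. The illustrative differences of 1.08 and 3.24 points rest on an assumed event rate and assumed attribution shares. For comparison, the chance standard deviation of the difference between arms at 5.4% and 500 per arm is √(2 × 0.054 × 0.946 / 500) = 1.43 points. A moderate attribution gap would therefore be smaller than chance variation, and a large one would exceed it.

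Two stronger readings should be resisted. One is that the rule favours the app: the extra routes to relatedness could raise the study arm's count, while a belief that the app is harmless could lower it, so the direction cannot be known. The other is that the primary result is compromised: all-cause readmission carries no relatedness filter, and the 794 does not change. A death without readmission is not a primary event, but that follows from the endpoint's definition, and the documents give no death rate from which to judge its effect.

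**What to change.** 1. Reconcile Section XII.D.2 with Section XIII.A so that relatedness is a recorded attribute and not a condition of being an AE or SAE. The Adverse Event Form already records relationship to the study device. If the Sponsor wants a shorter reportable list, give it its own name and keep it from defining AEs or SAEs.
2. State that the comparison in Section V, purpose 4, will tabulate by arm all deaths, hospitalisations, serious events and listed complications, whatever the attribution, with related events as a subset. Name the Medical Event Log and chart review as sources, and use the Study Completion Form to check deaths.
3. Reconcile the post-surgery start of collection and the Section IV schedule with the statement that events are documented throughout the investigation and with pre-operative App and Watch use. Whatever start point is chosen, use the same one in both RCT arms.
4. Optional: a sensitivity analysis of the primary endpoint that counts death by day 30 as an event.

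The cost is an amendment to the wording, tables drawn largely from data already collected, and a short pre-operative log entry if collection starts earlier. The downside is more Adverse Event Forms and higher stated event counts.
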